# 8. Analysis of the Secondary Endpoints

418 419

### 420 8.1 Secondary CGM Metrics

Summary statistics (mean ± SD or median (quartiles)) will be reported for the CGM-measured metrics at baseline and during follow up as well as for differences from baseline by treatment group. CGM metric differences between AID and Control Groups will be compared using a linear mixed effects regression model adjusting for the baseline value of the metric and clinical center (random effect). A separate variance will be modelled for each group. Residual values will be examined for an approximate normal distribution. If residuals are highly skewed, then a transformation or robust statistical method (e.g., nonparametric or M-estimation) will be used instead. Missing data will be handled using direct likelihood.

428 429

#### 430 8.2 Secondary Efficacy CGM Endpoints Included in Hierarchical Analysis

The following secondary endpoints will be tested for superiority, with a hierarchical testing approach toprotect the type 1 error rate as described in Section 16.

- HbA1c (primary outcome)
- Time in range 70-180 mg/dL
- Mean glucose
- Time >180 mg/dL
- Time >250 mg/dL
- CGM-measured prolonged hyperglycemia events (defined in Section 5.3)
- Time <70 mg/dL
- Time <54 mg/dL
- CGM-measured hypoglycemia events (defined in Section 5.3)
- Coefficient of variation
- 443

If the primary analysis for HbA1c described in Section 7 results in a statistically significant result (p < 0.05), then testing at the 0.05 level will proceed to the first outcome in the above list (i.e., time in range 70-180 mg/dL). This process continues iteratively moving to the next variable down on the list until a non-significant result is observed, or all 10 variables have been tested. If a non-significant result is encountered, then formal statistical hypothesis testing is terminated, and any variables lower on the list will not be formally tested.

- 450 Regardless of the results of the hierarchical testing, summary statistics appropriate to the distribution
- 451 will be tabulated by treatment group for each hierarchical outcome. A 95% confidence interval for the
- treatment group difference also will be calculated for all hierarchical outcomes listed above. However, a
- 453 confidence interval that excludes zero will not be considered a statistically significant result if an
- 454 outcome variable higher on the hierarchical list failed to reach statistical significance.
- 455

#### 456 **8.3 Meal and Exercise Challenges Analyses**

- There will be a descriptive and a formal comparison for the analyses during the meal and exercise
  challenge. First, the descriptive analyses for the selected glycemic mentioned in Sections 5.4 and 5.5 and
- 458 challenge. First, the descriptive analyses for the selected glycemic mentioned in Sections 5.4 and 5 459 insulin metrics mentioned in Section 5.2 will include summary statistics (mean  $\pm$  SD or median
- 40 (quartiles)), scatterplots, boxplots, and/or individual meals or exercise CGM and insulin tracings. Meals
- 461 will be grouped by the two periods (during plus up to 4hr after the end of meal and nighttime following
- the meal and until 6AM on the day following each challenge), type (lunch and dinner), amount of
- 463 carbohydrates, and announcement in the pump or not.
- Exercises analyses will be grouped by the two periods (during plus up to 2hr after the end of exercise
  and nighttime following the exercise and until 6AM on the day following each challenge); and
  additionally grouped by length, intensity, or type of exercise.
- Insulin metrics and any adverse events occurring during these challenges will be reported by type ofchallenge in addition to their being included in the overall safety analyses (Section 9).
- 469 The number of each challenge per participant will be tabulated.
- 470

- 471 For the formal analyses, the glycemic metrics during the nights following the meal challenge will be
- tabulated and compared with the corresponding metrics during 14 non-challenge nights calculated as
- 473 mentioned above in Section 5.4. A mixed linear model that adjusts for clinical center as random effect
- will be used for this purpose. A similar approach will be used for the exercise challenges.
- 475

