- Thirteen Weeks of Follow-up: All CGM data following the randomization will be included. 223 • Since the meal and exercise sessions are designed as challenges to the system and the data to be 224 analyzed for possibly induced safety events, the CGM data between the start of the meal or 225 exercise and 6:00AM next morning will be analyzed separately (see Sections 5.4 and 5.5 below) 226 and not included here. If the 13-week visit is more than 13 weeks after the randomization visit 227 for a participant, then the CGM data will be truncated at 13 weeks (i.e., 91 days). At least 168hr 228 229 of data during these 13 weeks of follow-up are required for the glycemic metrics to be calculated 230 and for a participant to be included in the glycemic analyses. These are either Tandem pump CGM data or Dexcom CGM data if obtained to fill any Tandem data gaps. 231
- All CGM metrics during baseline and follow-up periods will be calculated giving equal weight to
   each sensor reading for each participant.
- Calculation of CGM metrics for the treatment group comparisons will exclude the challenges and the period through 6AM on the day following the end of the challenge. CGM metrics during and following the challenges will be reported separately as described in Sections 5.4. and 5.5; while an overall analysis will be performed for all CGM data in the AID group (i.e., including the challenge data) as described in Section 17.
- CGM-measured prolonged hyperglycemia events are defined as ≥90 cumulative minutes with CGM glucose >300 mg/dL within a 120-minute period (the participant becomes eligible for another prolonged hyperglycemia event after the CGM glucose is <180 mg/dL for ≥15

   consecutive minutes).
- CGM-measured hypoglycemia events are defined as ≥15 consecutive minutes with CGM glucose <54 mg/dL (the participant becomes eligible for another hypoglycemia event after the CGM glucose is ≥70 mg/dL for ≥15 consecutive minutes). For each of these metrics, the number of events per week is calculated for each participant and each metric is then analyzed as a continuous variable as described below.

- 248 249

257

258

259

260

261

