### 250 **5.4 Calculation of CGM Metrics for Meal Challenges**

- The meal challenges will happen and the metrics will be calculated only during the 13 weeks of
   follow-up in the AID group, and are based on either Tandem pump CGM data or Dexcom CGM
   data if obtained to fill any Tandem data gaps.
- Will be calculated only if the meal challenge session was recorded on the CRF. The date-time of
   the challenge-related events, along with other relevant details about the challenge will be
   recorded on the CRF and will be tabulated.
  - All data between the start of the meal challenge and 6:00AM next morning will be included.
  - For each meal, two different periods will be considered, and two separate glycemic metrics will be calculated:
  - During and two hours following the end of the meal the period between the start and 4 hours following the end of meal as recorded on CRF, and
- 262 > Overnight following the meal the period between 4 hours following the end of the meal and 6:00AM next morning.

- At least 2hr (or 24 CGM readings) are required for each one of the two periods associated with an individual meal session for the CGM metrics to be calculated.
  - Each CGM reading during a meal session will be given equal weight.
- The unit of analysis is an individual meal challenge session and any participant with at least one meal challenge completed will be included in these analyses.
  - The metrics calculated and reported here will include % time below 54, 70, 70-180, above 180, 250, 300 mg/dL and mean glucose.
- The above glycemic metrics will be calculated during the night following the meal challenge (10PM to 6AM) and will be compared with the corresponding metrics calculated during 14 nights without any challenge in the previous two days. Nights prior to the challenge will be used if available, then nights subsequent to the challenge if needed to obtain 14 total nights. The nights will be pooled together when compared with the night following the meal challenge. At least 6hr of CGM data are required for the night following the meal challenge and at least 72hr are required for the pooled 14 nights for these metrics to be calculated and formally compared.

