#### 279 5.5 Calculation of CGM Metrics during Scheduled Exercise Challenges

- The exercise challenges will happen and the metrics will be calculated only during the 13 weeks
   of follow-up in the AID group, and are based on either Tandem pump CGM data or Dexcom
   CGM data if obtained to fill any Tandem data gaps.
  - Will be calculated only if the exercise session was recorded on the CRF. The date-times of the challenge-related events, along with other relevant details about the challenge will be recorded on the CRF and will be tabulated.
  - All data between the start of the exercise challenge and 6:00AM next morning will be included.
    - For each exercise, two different periods will be considered, and two separate glycemic metrics will be calculated:
      - During and two hours following the end of the exercise the period between the start and 2 hours following the end of exercise as recorded on CRF, and
      - Overnight following the exercise the period between 2 hours following the end of the exercise and 6:00AM next morning.
- At least 1hr (or 12 CGM readings) are required for each one of the two periods associated with an individual exercise session for the CGM metrics to be calculated.
  - Each CGM reading during an exercise session will be given equal weight.
    - The unit of analysis is an individual exercise session and any participant with at least one exercise challenge completed will be included in these analyses.
- The metrics calculated and reported here will include % time below 54, 70, 70-180, above 180, 250, 300 mg/dL and mean glucose.
- The above glycemic metrics will be calculated during the night following the exercise challenge (10PM to 6AM) and will be compared with the corresponding metrics calculated during 14 nights without any challenge in the previous two days as described above for meal challenges.
   The nights will be pooled together when compared with the night following the exercise challenge. At least 6hr of CGM data are required for the night following the exercise challenge and at least 72hr are required for the previous and pooled 14 nights for these metrics to be calculated and formally compared.
- 307

266

269

270

278

283

284

285 286

287

288

289

290

291

292

295

296

297

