### 6. Description of Statistical Methods

- 350 351
- 352 6.1. General Approach:

- All analyses comparing the AID arm with Control arm will follow intention-to-treatment (ITT) 353 • approach, which means participants will be analyzed in the treatment arm assigned by 354 randomization regardless of the actual system use. All randomized participants with any data will 355 be included in the primary analysis and secondary analyses. 356 In the unlikely event that an enrolled participant is later found to be ineligible, the participant 357 • will be excluded from all analyses. 358 • All covariates obtained on a continuous scale will be entered into the models as continuous 359 variables unless it is determined that a variable does not have a linear relationship with the 360 outcome. In such a case, categorization and/or transformation will be explored. 361 All p-values will be two-sided. 362 • Standard residual diagnostics will be performed for all analyses. If values are highly skewed, 363 then a nonparametric or robust regression using M-estimation will be used instead for the 364 primary and secondary outcomes. Previous experience suggests that no transformation, 365 366 nonparametric, or M-estimation analyses will be necessary for HbA1c, mean glucose, % time in range 70-180 mg/dL, or % above 180 mg/dL. Other outcomes like % below 54 mg/dL will likely 367 be skewed with a need for a transformation, nonparametric, or M-estimation. 368 369 370 **6.2 Analysis Cohorts** 371 372 373 Primary and Secondary Analyses: All randomized participants with any data will be included in the primary and secondary analyses. 374 • Any partial data (i.e., missing baseline or follow-up) will be handled using the maximum likelihood 375 method (see Section 7 below). 376 377 • All participants with at least one meal challenge and with the minimum amount of CGM data during these periods – as defined above in Section 5.4 - will be included in the corresponding meal analysis. 378 Similar for participants with at least one scheduled exercise and the exercise analyses. 379 380 381 Per Protocol (PP) Analyses: Per-protocol analyses will be performed for primary outcome and secondary hierarchical outcomes (see 382 Section 8.2 below) only if >5% of participants will be excluded. All of the following criteria must be 383 met for a participant to be included in the per-protocol analyses. The criteria are as follows: 384 385 • 13-week visit completed,
- No major protocol deviations, and

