693 694 695 696	CGM metrics will be computed over the entire 13 weeks of the trial (i.e. while including the challenge periods) in the AID group and compared with the baseline CGM metrics using paired t-tests or nonparametric approaches depending on the distribution of the data. Binary outcomes will be assessed using McNemar's test.
697	
698	Plots
699 700 701	Boxplots, scatterplots, and/or cumulative distribution plots will be generated for all primary, hierarchical, and insulin outcomes. Plots will be generated for any other outcomes or analyses where a visual display is considered helpful.

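### Comparing one challenge night with a 14-night pool biases SAP 6.1's skewness fallback towards less hypoglycaemia; SAP 8.3 also states no pairing or participant term

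*SAP*

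**What the plan says.** SAP 8.3 has a descriptive part and a formal part. The formal part compares glycaemic metrics on the night after a meal challenge with the same metrics on 14 non-challenge nights. The method given is "A mixed linear model that adjusts for clinical center as random effect", and exercise is to be handled similarly.

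The ingredients are in SAP 5.4 and 5.5:
- Unit: "The unit of analysis is an individual meal challenge session" and, for exercise, "The unit of analysis is an individual exercise session".
- Reference nights: "Nights prior to the challenge will be used if available, then nights subsequent to the challenge if needed".
- How they enter: "The nights will be pooled together when compared with the night following the meal challenge". The minimum is 6 hours of data for the single night and 72 hours for the pool.
- Metrics: the list includes % time below 54 mg/dL.

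Protocol 6.2 and 6.3 put the three challenges of each type on consecutive days, so a participant normally contributes three sessions per type against largely the same pool. Rescheduled sessions can have a different one.

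SAP 6.1 says that outcomes such as % below 54 mg/dL will probably "be skewed with a need for a transformation, nonparametric, or M-estimation". SAP 5.3 sets the challenge data apart so that they can be "analyzed for possibly induced safety events". For the other within-AID comparison, SAP 17 does state pairing: the full CGM data are "compared with the baseline CGM metrics using paired t-tests or nonparametric approaches".

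SAP 2 records the challenge-night tests as an addition to the protocol, and Protocol 11.15.3 plans only summary statistics. SAP 8.3, with 5.4 and 5.5, is therefore their whole specification.

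**The concern.** There are two separate issues.

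**Fallback for skewed metrics.** The two quantities compared have the same mean under no effect but very different shapes. One night is zero or a fairly large value; a 14-night average is spread over small positive values. Methods that do not compare means (ranks, logs, M-estimation) see a difference when there is none. It points towards less low glucose on challenge nights, so it can hide the signal that these data are kept to detect.

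**Standard error.** The text gives no row layout, pairing or participant effect. An analyst can follow it and either analyse session-minus-pool differences or stack challenge and reference values as separate rows. These choices give different standard errors and p-values.

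**Working it through.** The documents give no sample size, SE or power for this comparison, so there is no stated figure to reproduce.

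**Inputs from the documents:** about 200 AID completers (SAP 4); 20-25 centres (SAP 1); 3 sessions per type (SAP Table 2); 14 pooled nights (SAP 5.4); two-sided tests (SAP 6.1); pilot median time <54 mg/dL of 0.00% (Protocol 1.3).

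**Assumptions, not in the documents:** how often a night has any time <54; the share of single-night variance between participants (ICC); and the between-participant variance t of the challenge effect, in units of within-participant night variance.

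**1. Zero-heavy metric, no challenge effect**

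Let p be the chance that a night has any time <54, equal for everyone. A session difference is certainly negative when the challenge night is 0 and the pool is above 0: (1-p)(1-(1-p)^14). It can be positive only if the challenge night is above 0, which has chance at most p.

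| p | negative | positive, at most |
|---|---|---|
| 0.02 | 0.98 × (1-0.754) = 0.24 | 0.02 |
| 0.05 | 0.95 × (1-0.488) = 0.49 | 0.05 |
| 0.10 | 0.90 × (1-0.229) = 0.69 | 0.10 |

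Now let rates vary strongly between participants: beta with mean 0.02 and concentration 2. P(14 zero nights) is the product of (1.96+i)/(2+i) for i = 0 to 13, which is 0.911, so the pool is above 0 for only 9%. P(15 zero nights) = 0.911 × 15.96/16 = 0.909. The negative share is 0.98-0.909 = 0.071, against at most 0.02 positive. The imbalance is smaller but remains.

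Simulation results with no challenge effect:
- Signed-rank on session differences, mean rate 2-10%: rejects in about 57-100% of runs.
- Log-scale differences, same rates: 93-100%.
- Signed-rank on one mean difference per participant, mean rate 2-20%: 11-38%, nearly all towards less hypoglycaemia. Pairing and collapsing reduce the bias but do not remove it.
- A separate zero-inflated gamma set-up, for metrics like time <54, <70 and >250: signed-rank, rank-sum, log, square root and Huber M-estimation reject in 98-100%, always towards lower values on challenge nights. For time <54 the means were 0.151 and 0.148, the medians 0.00 and 0.04.
- A time-in-range-like metric: rank tests reject in 5-12%, so the problem there is mild.
- Raw-scale mean of one difference per participant: about 4-9%.

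**2. Standard error, roughly normal metric**

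Set within-participant night variance to 1, b = ICC/(1-ICC), and leave centre aside. Per participant, the true variance of the mean difference is 1/3 + 1/14 + t.

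*Stacked, pool repeated for each session.* Model variance is (2/3)[b + (1 + t + 1/14)/2].
- ICC 0.5, t 0: (2/3)(1.536) = 1.024; true 0.405; SE ratio √2.53 = 1.59 (type I error 0.2%).
- ICC 0.1, t 0: 0.431/0.405; ratio 1.03 (4.3%).
- ICC 0.1, t 1: 0.765/1.405; ratio 0.74 (14.8%).

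*Stacked, one pool row.* Model variance is (4/3)[b + (3(1+t) + 1/14)/4].
- ICC 0, t 1: 2.024/1.405; ratio 1.20.
- ICC 0.7, t 0: 4.135/0.405; ratio 3.20.
- Always too wide; type I error at most 1.9%.

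*Stacked with the pool repeated, plus a participant intercept.* The ratio is 0.93, 0.78, 0.70 and 0.62 at t = 0, 0.25, 0.5 and 1 (type I error 6.9% to 22.1%). Adding an intercept to stacked rows is therefore not a remedy.

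*Session differences with the centre effect fitted* (simulated). Type I error is 4.7-7.1% across complete and incomplete sets, and up to 7.6% with night-to-night autocorrelation of 0.3. The centre effect absorbs most of the participant clustering.

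**The case against.** The strongest reply is that SAP 8.3 prescribes nothing defective. It names a mixed linear model, which compares means. SAP 5.4 sets each session's night against its own pool, with data minimums for both, so matched differences are the natural reading and near nominal. On the raw scale, a centre-level t-test of session differences in the zero-heavy setting rejected in 3.7-7.5% of no-effect runs. All this stands. A reader might infer that the written model is invalid, or that ignoring participants must inflate false positives. The documents support neither: no layout is prescribed, and the stacked-layout error can go either way or cancel.

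Next, the fallback is conditional, SAP 6.1 words it for primary and secondary outcomes, and the challenge-night metrics are not in the SAP 5.2 list. But 8.3 sits under the heading for secondary endpoints, 6.1 applies residual diagnostics to all analyses, and it expects this very metric to need the fallback. If it is not meant to apply, 8.3 should say so.

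Finally, a 5% rate shared by everyone fits the pilot poorly: only 0.95^42 = 12% of people would have no such night in six weeks, yet the pilot median was 0.00%. That is fair, and the equal-rate table should be read as showing the mechanism. With uneven rates that leave most participants at zero, session-level signed-rank still rejected in more than half of runs.

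**Conclusion.** The concern holds, mainly for the fallback. If SAP 6.1 is applied to % time <54 mg/dL in the challenge-night comparison, the test is biased towards less hypoglycaemia with no true effect. Rejection is roughly 57-100% for signed-rank on session differences and over 90% for log-scale differences, assuming any time <54 on 2-10% of nights. The size depends on those rates; the direction follows from setting one night against a 14-night pool.

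The standard-error point is secondary. Pairing and participant clustering are unstated. Session differences are near nominal (about 5-8%). Stacked rows, which the wording also allows, give a wrong SE whose direction depends on variance components that the documents do not give.

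A reader might extend this to the trial's main conclusions, but the documents do not support that. The tests are AID-only, outside the hierarchy and in their own false-discovery-rate group (SAP 16). HbA1c, the hierarchy, the descriptive tables and adverse-event reporting are unaffected. It should be corrected because it is cheap and bears on a safety question.

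**What to change.** In SAP 8.3, for meal and exercise challenges separately, add text to this effect:

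> The formal comparison uses within-participant differences (each session's night minus that session's own pooled 14-night value) on the original scale. They are analysed either as one mean difference per participant with clinical center as random effect, or as session differences with participant within clinical center as random effects. For skewed metrics the mean difference is kept, with inference by participant-level bootstrap or participant-clustered robust standard errors. The rank, transformation and M-estimation fallback of Section 6.1 is not applied to single-night-versus-pool comparisons.

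One of the two models should be chosen before the data are seen. In SAP 5.4 and 5.5, say that the session is the unit for the descriptive tables and that sessions are clustered within participant in the formal comparison. A bolus-level fixed effect for meals is optional.

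Permuting the challenge label among a participant's individual nights is not advised. Challenge nights are normally consecutive, so nights are not exchangeable if autocorrelated; such a test rejected in about 6-12% of no-effect runs with autocorrelation.

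The cost is a few sentences and slightly more code, with no new data. One value per participant merges the three bolus levels, and the mean test may be mildly liberal for very rare events (about 4-9% in simulation).
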